#### **8.1.1 Primary Endpoint Analysis**

A two-sided alpha of 0.05 will be applied to the primary analysis of the primary endpoint.

The primary endpoint of this trial is change in eGFR (CKD-EPI) from pre-treatment baseline to post-treatment follow-up, annualized (divided) by subjects' trial duration.

This normalization is necessary, otherwise the treatment group having more dropouts or

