more earlier dropouts may assume an unfair advantage. However, in order to reduce the impact of the outliers created by the annualized eGFR change in early dropout subjects, all annualized changes of dropout subjects that are greater (or less) than the maximum (or minimum) of the annualized eGFR change of all on-treatment completers will assume the maximum (or minimum) value as their annualized eGFR changes used in the primary analysis. This is because of the possibility that annualization of very variable short-term data (one or two months) by requiring a multiplication factor of 12 or 6 can result in an exaggerated estimate of annualized eGFR change. Early examples showed that this cannot be adequately managed by simple weighting in the analysis. Therefore, restrictions on the maximum and minimum values observed in the on-treatment completer population can further buffer the untoward effects of such outliers. In addition, the analysis based on the unadjusted annualized eGFR changes will serve as a sensitivity analysis of the primary endpoint. To reduce the variation in this primary endpoint, the last 3 observations of eGFR up to placebo run-in are observed at baseline (screening and placebo run-in periods) and another first 3 observations are observed after one week of post-treatment follow-up during a two week interval (within a total of 3-weeks post-treatment follow-up). Although it was initially designed to have subjects come back in this two week period to have their eGFR measures, it turns out that not all subjects could achieve this in our clinical operation. In order to reduce excluding subjects in the primary analysis due to failing to have follow-up data within this two week period, the window to have follow-up eGFR observations is thus set to be from 7 to 40 days post the last dose of IMP. Because the primary endpoint is annualized eGFR change, extending the follow-up window does not change placebo subjects' primary endpoint, since the duration from baseline to follow-up would be extended as well. For tolvaptan subjects, this window definition is actually conservative, since a few days of no treatment would be added to the duration of tolvaptan treatment for the annualization. The average of the 3 eGFR values observed during the baseline period is set as the baseline and the average of the 3 eGFR values observed during post-treatment follow-up period is set as the renal function measurement post-treatment. The dates of baseline and post-treatment observations are also set to the median of the dates of the (up to) three baseline and the (up to) three post-treatment follow-up observations respectively, and the duration is equal to the date of post-treatment follow-up minus the date of baseline plus one. This duration is used in the calculation of the annualized change.

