(8) Observations in eGFR which are 50% larger than a subject's screening eGFR observations will be excluded from the primary and second efficacy analyses.

(9) The following method to derive the weight for the primary analysis is proposed if the number of eGFR observations is kept at 3 in the pre-treatment baseline period. In order to derive the weight used in the weighted analysis, the following model is considered:

$$y_{i,0,k} = \alpha_i + e_{i,0,k} \quad \text{where } k = 1, 2, K_{i,0} \quad (1)$$

$$y_{i,j,k} = \alpha_i + \delta_{i,j} + e_{i,j,k} \quad \text{where } k = 1, 2, K_{i,j} \quad (2)$$

where  $K_{i,0}$  is the number of eGFR observations during the pre-treatment baseline period for subject  $i$ , and  $K_{i,j}$  is the number of eGFR observations during the post-treatment follow-up period for subject  $i$ , with visit  $j$  as the visit Month 12 for completers or mapped regular visits for early dropouts.  $\alpha_i$  is a random variable for the "real" eGFR baseline of subject  $i$ , and this variable will be cancelled out for change from baseline.  $\delta_{i,j}$  is a random variable for change from pre-treatment baseline for subject  $i$  to visit  $j$ . These  $\delta_{i,j}$ s are normally distributed, with means being  $\delta_{p,j}$  for placebo subjects and  $\delta_{T,j}$  for tolvaptan subjects, and variance  $\sigma_{\delta,j}^2$ . These  $\delta_{i,j}$ s are supposed to be independent from subject to subject, and each subject has only one post-baseline visit  $j$  in the primary analysis. In addition,  $\alpha_i$ s are assumed iid normally distributed,  $e_{i,j,k}$  are assumed iid  $N(0, \sigma^2)$ , and all these random variables are mutually independent. Their average over the  $K_{i,0}$  observations at baseline and the  $K_{i,j}$  observations at post-treatment follow-up will be:

$$\bar{y}_{i,0} = \alpha_i + \bar{e}_{i,0}, \quad \text{where } \bar{e}_{i,0} \sim N(0, \sigma^2/K_{i,0}) \quad (3)$$

$$\bar{y}_{i,j} = \alpha_i + \delta_{i,j} + \bar{e}_{i,j}, \quad \text{where } \bar{e}_{i,j} \sim N(0, \sigma^2/K_{i,j}) \quad (4)$$

the distribution of their difference is:

$$\bar{y}_{i,j} - \bar{y}_{i,0} = \delta_{i,j} + \bar{e}_{i,j} - \bar{e}_{i,0} \sim N(., \sigma_{\delta,j}^2 + \sigma^2(1/K_{i,0} + 1/K_{i,j})), \quad (5)$$

where the mean of the normal distribution is  $\delta_{p,j}$  for placebo subjects and  $\delta_{T,j}$  for tolvaptan subjects.

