In order to estimate the variance components given in (5), a further assumption of all  $\sigma_{\delta,j}^2$ 's are equal, ie,  $\sigma_{\delta,j}^2 = \sigma_{\delta}^2$  is made, since there may not be enough subjects withdraw to stabilized the estimate of  $\sigma_{\delta,j}^2$  at some visits. In addition, it is assumed all subjects get 3 eGFR observations at baseline. This assumption is reasonable, since usually subjects follow protocol schedules more strictly at the beginning of the trial, and could simplify

the estimation of the variance components. Then, a formula of change from baseline can be written similar to (5) for the estimation of the variance components:

$$y_{i,j,k} - \bar{y}_{i,0} = \delta_{i,j} + e_{i,j,k} - \bar{e}_{i,0} \sim N(., \sigma_{\delta}^2 + \sigma^2(1 + 1/3)), \quad (6)$$

A mixed model with fixed effect factors of treatment nested within visit, replication (for the repeated observations at the post-treatment follow-up in eGFR) will be applied to change from baseline (as the average of the 3 pre-treatment eGFR observations) in eGFR observed at each replication. In this mixed model, replications at the post-treatment follow-up are considered as the repeated measurements, with a compound symmetric variance matrix structure. In this estimated variance-covariance matrix, the diagonal elements are the estimate of  $\sigma_{\delta}^2 + \sigma^2(1 + 1/3)$ , and the off diagonal elements are the estimate of  $\sigma_{\delta}^2 + \sigma^2(1/3)$ . Solving these two equations will get the estimates of  $\sigma_{\delta}^2$  and  $\sigma^2$ . With these variance component estimates, the variance given in formula (5) is estimated for each subject. Dividing the estimated variance given in (5) by the subject's trial duration will provide an estimated variance for the subject's annualized change in eGFR. The inverse of this estimated variance will be the weight of the subject used in the primary analysis.

SAS code for the estimation of variance component

```
PROC MIXED ;
  CLASS SUBJECT VISIT TREATMENT REPLICATION ;
  MODEL CHANGE = TREATMENT (VISIT) REPLICATION ;
  REPEATED REPLICATION / TYPE=CS SUB=SUBJECT ;
RUN ;
```

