$$\bar{y}_{i,0} = \alpha_i + \bar{e}_{i,0}, \quad \text{where } \bar{e}_{i,0} \sim N(0, \sigma^2/K_{i,0}) \quad (3)$$

$$\bar{y}_{i,1} = \alpha_i + \delta_i + \bar{e}_{i,1}, \quad \text{where } \bar{e}_{i,1} \sim N(0, \sigma^2/K_{i,1}) \quad (4)$$

the distribution of the change from baseline for subject  $i$  is:

$$\bar{y}_{i,1} - \bar{y}_{i,0} = \delta_i + \bar{e}_{i,1} - \bar{e}_{i,0} \sim N(., \sigma_\delta^2 + \sigma^2(1/K_{i,0} + 1/K_{i,1})) \quad (5)$$

The estimation of  $\sigma^2$  is simply provided by:

$$v_e = \frac{1}{2} \{ \sum_i \sum_k (y_{i,0,k} - \bar{y}_{i,0})^2 / \sum_i (K_{i,0} - 1) + \sum_i \sum_k (y_{i,1,k} - \bar{y}_{i,1})^2 / \sum_i (K_{i,1} - 1) \} \quad (6)$$

where  $\sum_i$  sums over all subject  $i$ , and  $\sum_k$  sums over all replicate  $k$  for subject  $i$ , either at baseline visit or post-treatment follow-up visit. Let

$$d_i = (\bar{y}_{i,1} - \bar{y}_{i,0}) / t_i \sim N(., [\sigma_\delta^2 + \sigma^2(1/K_{i,0} + 1/K_{i,1})] / t_i^2) \quad (7)$$

being the annualized change from baseline of subject  $i$  and its distribution, where  $t_i$  is the trial duration to annualize the primary endpoint for subject  $i$ , with mean  $\beta_T$  and  $\beta_P$  for tolvaptan and placebo subjects respectively. Let

$$\tau_i = [\sigma_\delta^2 + \sigma^2(1/K_{i,0} + 1/K_{i,1})] / t_i^2 \quad (8)$$

The treatment averages are:

$$\bar{d}_T = \sum_{i \text{ in TLV}} d_i / n_T \quad \text{and} \quad \bar{d}_P = \sum_{i \text{ in PLC}} d_i / n_P \quad (9)$$

where  $\sum_{i \text{ in TLV}}$  ( $\sum_{i \text{ in PLC}}$ ) sums over all tolvaptan (placebo) subjects, and  $n_T$  ( $n_P$ ) is the total number of subjects in tolvaptan (placebo). Let

$$v = \frac{1}{2} \{ \sum_{i \text{ in TLV}} (d_i - \bar{d}_T)^2 / (n_T - 1) + \sum_{i \text{ in PLC}} (d_i - \bar{d}_P)^2 / (n_P - 1) \} \quad (10)$$

Since

$$\begin{aligned} \sum_{i \text{ in TLV}} (d_i - \bar{d}_T)^2 &= \sum_{i \neq i' \text{ in TLV}} (d_i - d_{i'})^2 / 2n_T \text{ and} \\ \sum_{i \text{ in PLC}} (d_i - \bar{d}_P)^2 &= \sum_{i \neq i' \text{ in PLC}} (d_i - d_{i'})^2 / 2n_P \end{aligned} \quad (11)$$

formula (10) can be rewritten as:

$$v = \sum_{i \neq i' \text{ in TLV}} (d_i - d_{i'})^2 / [4n_T(n_T - 1)] + \sum_{i \neq i' \text{ in PLC}} (d_i - d_{i'})^2 / [4n_P(n_P - 1)] \quad (12)$$

and

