$$\begin{aligned} E(v) &= \sum_{i \neq i' \text{ in TLV}} (\tau_i + \tau_{i'}) / [4n_T(n_T - 1)] + \sum_{i \neq i' \text{ in PLC}} (\tau_i + \tau_{i'}) / [4n_P(n_P - 1)] \\ &= \sum_{i \neq i' \text{ in TLV}} \{ [\sigma_\delta^2 + \sigma^2(1/K_{i,0} + 1/K_{i,1})] / t_i^2 + [\sigma_\delta^2 + \sigma^2(1/K_{i',0} + 1/K_{i',1})] / t_{i'}^2 \} / [4n_T(n_T - 1)] \\ &+ \sum_{i \neq i' \text{ in PLC}} \{ [\sigma_\delta^2 + \sigma^2(1/K_{i,0} + 1/K_{i,1})] / t_i^2 + [\sigma_\delta^2 + \sigma^2(1/K_{i',0} + 1/K_{i',1})] / t_{i'}^2 \} / [4n_P(n_P - 1)] \\ &= \sum_{i \text{ in TLV}} \{ [\sigma_\delta^2 + \sigma^2(1/K_{i,0} + 1/K_{i,1})] / t_i^2 \} / (2n_T) + \sum_{i \text{ in PLC}} \{ [\sigma_\delta^2 + \sigma^2(1/K_{i,0} + 1/K_{i,1})] / t_i^2 \} / (2n_P) \\ &= \delta^2 [\sum_{i \text{ in TLV}} 1 / (2n_T t_i^2) + \sum_{i \text{ in PLC}} 1 / (2n_P t_i^2)] \\ &+ \sigma^2 [\sum_{i \text{ in TLV}} (1/K_{i,0} + 1/K_{i,1}) / (2n_T t_i^2) + \sum_{i \text{ in PLC}} (1/K_{i,0} + 1/K_{i,1}) / (2n_P t_i^2)] \end{aligned} \quad (13)$$

where  $E(v)$  is the expectation of  $v$ . Thus, the estimate of  $\sigma_\delta^2$  is:

$$\begin{aligned} v_\delta &= \{ v - v_e [\sum_{i \text{ in TLV}} (1/K_{i,0} + 1/K_{i,1}) / (2n_T t_i^2) + \sum_{i \text{ in PLC}} (1/K_{i,0} + 1/K_{i,1}) / (2n_P t_i^2)] \\ & / [\sum_{i \text{ in TLV}} 1 / (2n_T t_i^2) + \sum_{i \text{ in PLC}} 1 / (2n_P t_i^2)] \} \end{aligned} \quad (14)$$

And the estimated variance of the annualized change from baseline for subject  $i$  ( $d_i$ ) is:

$$[v_\delta + v_e (1/K_{i,0} + 1/K_{i,1})] / t_i^2 \quad (15)$$

The reciprocal of (15) will be the weight for subject  $i$  used in the weighted analysis.

(11) Mapping of unscheduled visit and end of treatment visit during double-blind treatment period to nominal visits: In general, these visits will be mapped into the monthly nominal visits based on the mid-point between two monthly visits, ie, if an unscheduled visit or an end of treatment visit is within 15 days of the previous visit, it will be mapped to the previous visit; if it is greater than 15 day of the previous visit, it will be mapped to next appropriate visit, with 30.5 days (round if necessary) between each two adjacent nominal visits. If an unscheduled visit or an end of treatment visit falls into 351 (rounded from 30.5x11 + 15) to 381 (= 366 + 15) days post-randomization, it

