## 210 ANOVA Table of Change from Baseline on eGFR Follow-up Observations

## Post Treatment Follow-up Visits 1, 2, and 3

Source	DF	SS	MS	F-value	P-value
Between	9	1709.75	189.97	14.81	<.0001
Within	15	192.36	12.82		
Corrected Total	24	1902.10			

Because the mean sum square of within-subject error (12.82) in study 210 is only ~6.7% of the mean sum square of between-subject error (189.97), we may conclude that the increase of eGFR observations (use of more than one observation) does not reduce the variance of their average much, since increased numbers of observations only reduce the within-variance component in their average, and there is little within-subject variation to be further reduced.

Since the 210 eGFR data used for this blinded sample size re-calculation are based on Rate Blank serum creatinine, this fact may raise the question of whether the within-subject errors of these two kinds of serum creatinine are very different or not. It is likely that Rate Blank serum creatinine is more stable with less within-subject variation. Indeed, this was considered an advantage of the Rate Blank method when our central lab vendor, Covance, recommended it to us. Thus, it is not known whether the small within-subject error in 210 is caused by Rate Blank data or is actually occurring in 210 eGFR data. Because of this, there are no grounds for making any changes to the number of eGFR observation at pre-treatment baseline and post-treatment follow-up visits, unless 210 eGFR data based on Enzymatic serum creatinine are available. Based on the current clinical operation plan, Enzymatic serum creatinine data are only available when subjects finish their 12-month visits as well as their post-treatment follow-up visits (for both completer and early withdrew subject), since batched analysis on frozen blood samples of all visits would only be done after that. Thus, more appropriate analysis to determine the number of eGFR observations at pre-treatment baseline and post-treatment follow-up visits can only be provided after more subjects complete the study.

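### SAP 8.3(9) weights the primary ANCOVA as if the variance of change/t were V/t; under its own model it is V/t², as item (10) has it

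*SAP*

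**What the plan says.** SAP 8.1.1 defines the primary endpoint as the eGFR change from pre-treatment baseline to post-treatment follow-up, "annualized (divided) by subjects' trial duration". It is analysed by weighted ANCOVA, with weight equal to the reciprocal of the estimated variance of that annualized value.

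SAP 8.3 gives two recipes for the weight.

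- **Item (9)** "is proposed if the number of eGFR observations is kept at 3 in the pre-treatment baseline period". Its formula (5) gives the variance of the change as V = σ_δ² + σ²(1/K₀ + 1/K_j), with σ_δ² set equal at all visits. It continues: "Dividing the estimated variance given in (5) by the subject's trial duration will provide an estimated variance" of the annualized change, and the inverse of that is the weight.
- **Item (10)** is for use only if the blinded re-estimation alters the number of baseline draws. It has the same V and the same common σ_δ². It says that t_i "is the trial duration to annualize the primary endpoint for subject" i, and it divides by t_i² in formulas (7), (8) and (15). Then: "The reciprocal of (15) will be the weight for subject" i.

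The re-estimation memorandum in Appendix 5 concluded that "there are no grounds for making any changes to the number of eGFR observation at pre-treatment baseline and post-treatment follow-up visits", and 8.1.1 averages three baseline values. Item (9) therefore applies.

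Section 8.1.1 also caps extreme values: dropouts whose annualized change lies outside the range of the on-treatment completers "will assume the maximum (or minimum) value as their annualized eGFR changes used in the primary analysis".

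**The concern.** Dividing a random variable by a known t divides its variance by t². Item (9) divides by t and calls the result the variance of the annualized change. That does not follow from its own equal-variance assumption, and it disagrees with item (10). The two items differ in how the variance components are estimated and in whether the number of baseline draws is constant. Neither difference justifies another power of t.

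This is the confirmatory test. The subjects who receive too much weight are the early discontinuers, the same subjects whose annualized values 8.1.1 describes as unstable. The PROC GLM code names only a WEIGHT variable, so the sentence in item (9) is the instruction a programmer would follow. A programmer who corrects it and one who follows it literally would in general get different primary p-values.

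**Working it through.** **Inputs.** σ² = 7.1, σ_δ² = 28.05 and effect 1.07 (protocol 7.1.1); two-sided alpha 0.05, 10% dropout, about 1300 subjects, 1:1. Baseline lies about 6 weeks before randomization and follow-up about 2 weeks after treatment ends (SAP 4.1).

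**The plan's own sample size.** V = 28.05 + 2 × 7.1/3 = 32.78. Per arm, 2 × (1.960 + 1.282)² × 32.78 / 1.07² ≈ 602. Then 602/0.9 ≈ 669, or 1338 in total, against 1336 in the plan's table. The inputs are therefore read correctly. This figure does not involve the weights.

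**Relative weights.** t = months on randomized treatment/12 + 8/52 years. A completer has t = 1 + 0.154 = 1.154. The excess weight is t_completer/t.

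| Stops at | t (years) | Weight relative to a completer, item (9): t/1.154 | With t²: (t/1.154)² | Excess |
|---|---|---|---|---|
| just after randomization | 0.154 | 0.133 | 0.018 | 7.5× |
| 1 month | 0.237 | 0.206 | 0.042 | 4.9× |
| 3 months | 0.404 | 0.350 | 0.122 | 2.9× |
| 6 months | 0.654 | 0.567 | 0.321 | 1.8× |

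**Effect on the test, no cap, constant V.** Assumptions: 650 per arm; 10% discontinue in each arm and all have follow-up; no covariates; the effect accrues at 1.07 per randomized year, so a completer's expected difference is 1.07/1.154 = 0.927. Within an arm, the true variance of the weighted mean is Σw²(V/t²)/(Σw)². The model-based variance is the estimated residual scale divided by Σw.

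| | Dropout even over months 1–11 | All dropout in months 1–3 |
|---|---|---|
| Expected difference, t v t² | 0.921 v 0.924 | 0.916 v 0.924 |
| True SE, t v t² | 0.2879 v 0.2846 | 0.2968 v 0.2890 |
| Model SE, t v t² | 0.2967 v 0.2846 | 0.3221 v 0.2890 |

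Even dropout:
- The model variance with t weights is (0.2967/0.2879)² = 1.06 times the true one.
- Type I error is 2Φ(−1.96 × 0.2967/0.2879) = 4.3%.
- Power with t is Φ(0.921/0.2879 − 1.96 × 0.2967/0.2879) = Φ(1.18) = 88.1%.
- Power with t² is Φ(0.924/0.2846 − 1.96) = Φ(1.29) = 90.1%.
- With t weights and a correct SE, power would be Φ(0.921/0.2879 − 1.96) = 89.2%. About 0.9 point is therefore lost efficiency; the rest comes from the oversized SE.

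Months 1–3:
- The variance ratio is (0.3221/0.2968)² = 1.18, and type I error is 3.3%.
- Power with t is Φ(0.916/0.2968 − 1.96 × 0.3221/0.2968) = Φ(0.96) = 83.1%.
- Power with t² is Φ(0.924/0.2890 − 1.96) = Φ(1.24) = 89.2%.

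**With the cap of 8.1.1** (simulation, 20,000 trials per cell, placebo slope −4.5 per year, otherwise as above):

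| | Power, t v t² | Type I error, t v t² |
|---|---|---|
| Even dropout | 88.8% v 90.0% | 4.8% v 5.3% |
| Months 1–3 | 87.8% v 90.4% | 4.5% v 5.5% |

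**If V is not constant.** If Var(change) grew in proportion to t, dividing by t would be right. Uncapped power would then be 90.5% v 91.0% (even) and 89.4% v 90.6% (months 1–3), with type I error of 5.0% with t and 5.4% and 5.8% with t².

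The blinded by-visit SDs in Appendix 5 (Table 3, months 1–7) suggest growth of about t^0.19 (SE 0.11). After removal of an assumed error variance of 7.1 × 4/3 = 9.47, the exponent is 0.33 (SE 0.17). Both are nearer 0 than 1. At t^0.3, uncapped, power is 89.1% v 90.5% (even) and 86.0% v 89.9% (months 1–3), with type I error of 4.6% v 5.2% and 3.9% v 5.4%.

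**The case against.** **The cap matters most.** It is part of the primary analysis and shrinks the variance of early dropouts' values, so the uncapped ratios overstate the error. On one capped calculation, the ideal weight relative to a completer is about 0.14 at month 1, 0.17 at month 2, 0.20 at month 3 and 0.36 at month 6. Item (9) gives 0.206, 0.278, 0.350 and 0.567; t² gives 0.042, 0.077, 0.123 and 0.321. Item (9) is nearer at months 1 and 2, the two are about equally far off at month 3, and t² is nearer by month 6. Part of the capped power gain from t² also comes from its size exceeding 5%. A size-adjusted simulation (12,000 trials per cell) gave 90.1% v 90.4% for even dropout and 88.6% v 89.2% for months 1–3. This stands: it limits the consequence and is the reason for a robust SE.

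**Only one item applies.** Items (9) and (10) have mutually exclusive conditions, so the plan does not formally offer two primary p-values. That is correct. But the item that applies is the one that does not follow from its model.

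**It may be a slip of wording.** The program may already use t². The documents do not show it. If so, the sentence still has to be corrected so that plan and program agree.

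**The size depends on assumptions.** With an effect of 1.07 on the annualized scale, instead of per randomized year, the even-dropout powers are 95.5% v 96.4%, a loss of 0.9 point. The sample size calculation treats the 10% as lost, whereas here they all contribute. The exponents from Appendix 5 rest on pooled, on-treatment, Rate Blank data, with visits treated as independent. All of this bears on the size of the effect and none of it on the algebra.

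**Conclusion.** The concern holds: item (9) is wrong as written. Its stated model gives V/t², and its instruction gives V/t. Only variance growing in proportion to t would justify the instruction, and item (9) assumes the opposite without offering that rationale.

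The consequence is moderate. There is essentially no bias and, under the SAP's model, no inflation of type I error. For the capped primary analysis at 10% discontinuation the nominal power loss is about 1 to 3 points, and under one point at equal size. For the unadjusted sensitivity analysis it is about 2 to 6 points. These figures assume that all discontinuers have follow-up and ignore covariates; the loss is larger when stopping is early.

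This should be fixed because the weight of the confirmatory analysis must have one correct definition before the data are unblinded. The likely loss of power is the lesser reason.

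**What to change.** In SAP 8.3(9), state that formula (5) is divided by the square of the subject's trial duration in years. The weight becomes t_i² / [σ_δ² + σ²(1/K_i0 + 1/K_ij)], the same form as the reciprocal of formula (15) in item (10). Confirm before unblinding that the program computes this.

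Add a sandwich SE for the primary contrast as a sensitivity analysis. With t² weights, type I error came out at about 5.2% to 5.8% where the cap binds or the variance grows with time.

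The cost is one phrase in the SAP, one line of code to check and one extra SE. No new data are needed.

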#### 8.4 Subgroup Efficacy Analysis

Subgroup analyses will be provided to the primary and the key secondary endpoints by region (US and non-US), gender (male and female), race (Caucasian and Other races), age ( $\leq 55$  years or not), baseline GFR level [REDACTED], and baseline Total Kidney volume [REDACTED], and by CKD Stage.

